### 6.2 Endpoints

Study Objectives	Primary objective
------------------	-------------------

## Part 1

	Part 1To identify the optimal single dose of rac-PZQ ODT or L-PZQ ODT formulation which has a clinically meaningful cure rate (as assessed by Kato-Katz method) and an acceptable safety profile in 2 to 6year- old children infected with S. mansoni .Part 2To evaluate the efficacy and safety of the selected ODT formulation (L-PZQ or rac-PZQ) from Part 1 at the appropriate adjusted dose(s) in infants aged 3 to 24 months infected with S. mansoni .
	Secondary objectives
	$\frac{Part 1}{T}$
	• To determine the safety of different doses of rac-PZQ and L-PZQ ODTs in children aged 2 to 6 years infected with S. mansoni
	• To explore the dose-exposure-response relationship for L-PZQ, D-PZQ and rac-PZQ in children aged 2 to 6 years infected with S. mansoni
	• To assess the efficacy and safety of rac-PZQ commercial tablet at 20 mg/kg t.i.d. dose administration and at 40 mg/kg single dose administration in children aged 2 to 6 years infected with S. mansoni
	• To assess the acceptability in terms of ease of administration of the rac-PZQ ODTs and L-PZQ ODTs in children aged 2 to 6 years infected with S. mansoni
	Part 2
	• To assess the acceptability in terms of ease of administration of the selected ODTs (rac-PZQ or L-PZQ) in 3- to 24-month infants infected with S. mansoni
	• To explore the dose-exposure-response relationship for L-PZQ, D-PZQ and rac-PZQ in 3- to 24-month infants infected with S. mansoni
Study design and plan	This is a phase II study consisting of two parts (Part I and Part 2Part 2 will only start once Part 1 is completed. The study will be conducted at the district hospital of PPD . An additional site at PPD , may be added depending on patients' recruitment rate.

	
 
Part 1 is an open-label, randomized, controlled, dose finding study with three formulations of PZQ (commercial rac-PZQ tablets, oral disintegrating tablets of rac-PZQ and L-PZQ) in children aged 2-6 years infected with S. mansoni. Subjects will be randomized to one of the following arms:
 
C1: commercial rac-PZQ tablets (Biltricide®) at 20 mg/kg dose t.i.d. (three times a day)
 
C2: commercial rac-PZQ tablets (Biltricide®) at 40 mg/kg single dose
 
C3: rac-PZQ ODTs at 40 mg/kg single dose
 
C4: rac-PZQ ODTs at 60 mg/kg single dose
 
C5: L-PZQ ODTs at 45 mg/kg single dose
 
C6: L-PZQ ODTs at 45 mg/kg single dose
 
C7: L-PZQ ODTs at 60 mg/kg single dose
 

	
 
approval while randomisation for the other groups can continue to 40 subjects per arm.
 
Part 2 will run after all subjects in Part 1 (C1-C6/7) have completed and are reviewed by the SMC. A cohort with infants of 13-24
 

	months infected with S. mansoni (C8) and a cohort with infants of 3-12 months infected with S. mansoni (C9) will be enrolled in an age-staggered approach.
	Infants in cohort C8 will be treated with rac-PZQ or L-PZQ ODTs at the optimal dose level selected by SMC from Part 1 (based on benefits-risks evaluation). In addition, a maturation factor will also be included (if applicable) to decide on the dose for these infants.
	After 10 infants age 13 to 24 months have been enrolled, the overall safety and efficacy data in these patients will be evaluated by the SMC for the decision to include the lower age group of infants (cohort C9). SMC will also decide whether dose level adaptations are needed before starting enrolling C9.
Planned number of subjects	Total number of subjects: 360-420 (if C7 is included) enrolled subjects in Part 1 and 40 enrolled subjects in Part 2. Number of subjects per treatment arm:
	Part 1: 60 enrolled subjects in each cohort (C1 to C7)

	Part 2: 30 enrolled subjects in the 13-24 months cohort (C8)
	10 enrolled subjects in the 3-12 months cohort (C9)
Primary endpoint	Clinical cure defined as no parasite eggs in the stools ( S. mansoni infections)14-21 days after treatment. Egg counts will be determined by the Kato-Katz method.
Secondary endpoints	Efficacy endpoints
	• Egg Reduction Rate (ERR, %) calculated based on the arithmetic (and geometric) mean egg count per gram of stool (epg) before and 14-21 days after treatment (as determined by Kato-Katz method).
	• Cure defined as absence of parasite antigens in the urine as assessed by the commercially available POC-CCA test for S. mansoni
	Safety and tolerability endpoints
	• Changes in laboratory safety parameters and vital signs (body temperature, blood pressure and pulse rate)
	• Occurrence, nature, severity and outcome of adverse events
	Occurrence of Adverse Drug Reactions per treatment group
Pharmacokinetics	Originally, a PK profile of L-PZQ, D-PZQ and rac-PZQ (AUC 0-t , $C_{max}$ , $t_{max}$ , $t_{lag}$ , AUC 0-<math>\infty</math> , AUC extra , $t_{\frac{1}{2}}$ , $\lambda_z$ , CL/f and $V_z/F$ ) was to be produced, followed by assessment in 25% of the subjects of cohorts C1-C7 with a rich sampling scheme and in 75% of the subjects with a sparse sampling scheme.
	Further, PK would have been assessed in all subjects of Part 2 (cohorts C8 and C9) with a rich sampling scheme. Due to technical challenges in the preparation of the PK samples, it was decided by the Sponsor that no PK variable calculations will be done. The data will only be listed, and not analysed.
	The planned PK analysis is pending resolution of technical problems with previously validated DBS bioanalytical assay. Depending on the outcome, the PK data may potentially just be listed and not analysed.
Diagnosis	Screening diagnosis of S. mansoni infection will be done using a single POC-CCA urine cassette test. Briefly, one urine sample will be collected from each subject and evaluated with a commercially available POC-CCA cassette test.
	Subjects who are positive for POC-CCA test will provide stool samples to assess infection intensity using the Kato-Katz method.

Subjects will be tested for S. haematobium in order to exclude S. mansoni/S. haematobium co-infections.
Kato-Katz diagnosis of S. mansoni infection : two stool samples will be collected from each subject on different days within a maximum of five days, at screening, as baseline and 14-21 days after dosing (for treatment efficacy assessment). Three Kato-Katz thick smears (41.7 mg) will be prepared from each stool sample and read under a microscope following the instructions of the Kato-Katz manual from the World Health Organization. Infection intensity (expressed as egg count per gram of stool (epg)) will be calculated for each. S. mansoni positive diagnosis is defined as positive egg counts of S. mansoni in stool (>1 egg/1 occasion) according to the WHO classification: light (1-99 eggs per gram of faeces), moderate (100-399 mg eggs per gram of faeces) and heavy ( $\geq$ 400 eggs per gram of faeces) infections.
Diagnosis of S. haematobium infection will be made by urine examination using the filtration technique. One urine sample will be collected from each subject at screening. 10 ml of urine samples will be filtered through a filter mesh which will be then examined under the microscope for S. haematobium egg count. S. haematobium positive diagnosis is defined as positive egg counts of S. haematobium in urine (1 egg/10 ml of urine).

## 7 Sample Size/Randomisation

## 7.1 Sample Size

Part 1: this study is exploratory. There is no hypothesis testing.

The sample size is based on the minimum number of subjects to reach a meaningful precision of the primary efficacy endpoint estimate (cure rate) in each arm, considering the stratification factor.

There are limited historical data on the impact of the severity of infection on the observed cure rate. In the recent study by Keiser et al. (unpublished data), the observed cure rate in *S. mansoni* infected children varied between 55% and 60% in moderately infected children and 70% and 85% in light infected children depending on the dose. The table below presents the overall cure rate projections according to different assumptions of true cure rate in mild (low) and moderately infected children.

Overall cure rate (95%CI),	Assump	tions of Cure F	Rate in Light In	fections
(N=50)	70%	75%	80%	85%

	50%	62% (48%, 74%)	65% (52%, 78%)	68% (56%, 80%)	71% (60%, 82%)
Assumptions of	55%	64%	67%	70%	73%
Cure Rate in		(50%, 76%)	(54%, 80%)	(58%, 82%)	(62%, 84%)
Moderate/Heavy	60%	66%	69%	72%	75%
Infections		(52%, 78%)	(56%, 80%)	(60%, 84%)	(64%, 86%)
	65%	68% (54%, 80%)	71% (58%, 82%)	74% (62%, 86%)	77% (66%, 88%)

A minimum-clinical meaningful cure rate is considered as equal to 70%. With 50 evaluable patients enrolled, stratified as 40% moderate/heavy and 60% light, the corresponding 95% CI lower bound of an observed cure rate of 70% would be above ~58%, depending on potential difference between the strata. This sample size would also provide the minimum number of subjects to estimate the cure rate within strata.

Considering the efficacy criteria for the selection of the dose (observed cure rate >70%), through simulations, the table below presents the probability of observing an overall cure rate >= 70% based on different scenarios of true cure rates based on different strata, assuming a stratification of 40% moderate/heavy infections and 60% light infections.

Probability of observ	ring a	Assumptio	ns of Cure I	Rate in Ligh	t Infections
cure rate $\geq 70\%$ , N	=50,	70%	75%	80%	85%
	50%	15%	27%	45%	64%
Assumptions of Cure Rate in	55%	23%	38%	57%	76%
Moderate/Heavy Infections	60%	33%	51%	70%	85%
intections	65%	45%	63%	80%	92%

For instance, a sample size of 50 evaluable subjects provides a probability of around 85% to observe a cure rate of  $\geq$ =70% if the overall true cure rate is 75% with 40% of moderate/heavy and 60% of light infections.

Assuming an approximately 17% dropout rate, 60 subjects per arm will be randomized to ensure at least 50 evaluable subjects per arm.

Part 2: 30 subjects infected with *S. mansoni* aged 13 to 24 months (C8) and 10 subjects infected with *S. mansoni* aged 3 to 12 months (C9) will be included to evaluate tolerability and efficacy

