Reference therapy	Rac-PZQ oral tablets (Biltricide® 600 mg) in crushed form					
	Mode of administration: the tablets (scored) will be divided into 150 mg parts, crushed, suspended in water and the solution will be swallowed after a meal.					
	Doses: 20 mg/kg t.i.d. dose given every 4 hours (cohort C1) and 40 mg/kg single dose (cohort C2)					
Planned trial and treatment duration per subject	Maximum 28 days of pre-screening and screening period, followed by 1 day treatment and 14-21 days of follow-up period.					
	Total duration per subject: up to 7 weeks.					
Statistical methods	All efficacy and safety endpoints will be analysed descriptively. Point estimation and 95% confidence interval (CI) will be calculated for primary and secondary efficacy endpoints for each treatment					

arm. The calculation of 95% CIs for proportions will rely on the Clopper-Pearson (exact) method.

The primary efficacy endpoint will be presented as cure rate (Kato-Katz method). For each treatment arm, the cure rate will correspond to the percentage of subjects becoming egg-negative 14-21 days after treatment with the study drug. Criteria for dose selection will be described in a SAP prior to first patient first dose.

Secondary endpoints will be described by treatment arms:

- Mean Egg Reduction Rate (ERR, %) 14-21 days after treatment (Kato-Katz method)
- Cure rate (POC-CCA method) as assessed by the absence of parasite antigens as determined in urine with the commercially available POC-CCA assay for *S. mansoni*

Sample size estimation

This study is exploratory. There is no null hypothesis tested.

Part 1: the sample size is based on the precision of the 95% CI of the cure rate (Kato-Katz method) in each arm. A cure rate of 70% is considered as the minimum-clinically meaningful threshold. A sample size of 50 evaluable subjects provides a probability of around 85% to observe a cure rate of \geq 70%, if the overall true cure rate is 75% (assuming 40% of moderate/heavy and 60% of light infections). Assuming an approximately 17% dropout rate, 60 subjects per arm will be randomized to ensure at least 50 evaluable subjects per arm.

Part 2: 30 subjects aged 13 to 24 months infected with *S. mansoni* (C8) and 10 subjects aged 3 to 12 months infected with *S. mansoni* (C9) will be included to evaluate drug tolerability and efficacy.

2 Sponsor, Investigators and Trial Administrative Structure

This clinical trial will be sponsored by:

Merck KGaA

[name]

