#### Significance level:

All statistical tests mentioned in this SAP are to be regarded as exploratory. All statistical tests comparing treatment arms will be performed two-sided. If confidence intervals are to be calculated, these will be two-sided with a confidence probability of 95%, unless otherwise specified in this SAP.

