### **Overall clinical cure rate:**

Subjects cured of infection during the trial will be labelled as "responders". Responders will be defined as subjects with no parasite eggs (as determined by Kato-Katz method) in the End of Study

stool samples, 14-21 days after treatment, according to the eCRF page "Follow-up visit on D14-D21". Responders and non-responders will be coded as follows:

- For responders, *response* = 1
- For non-responders, response = 0

If the End of Study Kato-Katz egg count is missing, it will be imputed using the Last Observation Carried Forward (LOCF) approach. Subjects with missing data will be considered non-responders.

The proportion of responders in each cohort will be determined based on a binomial distribution. Exact 95% CIs will be calculated based on the Clopper-Pearson method. The PROC FREQ procedure in SAS will be used with the appropriate BINOMIAL and EXACT statements for point estimates and corresponding 95% CIs.

Point estimates and corresponding 95% CIs will be presented for cure rate, in terms of proportion of responders, by cohort. Response will be listed by cohort and subject. Estimates of cure rate will be presented graphically in the form of forest plots presenting means and 95% CIs.

Results will be presented for each analysis set.

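### The stated 95% CI lower bound of about 58% at an observed 70% cure rate (N=50) is not what the planned Clopper-Pearson interval gives; that bound is 55.4%

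*SAP*

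**What the plan says.** Both documents tie the Part 1 arm size to precision. SAP 7.1 says the size is the minimum number needed "to reach a meaningful precision of the primary efficacy endpoint estimate (cure rate) in each arm". The sample size paragraph of the Protocol Synopsis says "the sample size is based on the precision of the 95% CI of the cure rate (Kato-Katz method) in each arm". Neither tests a hypothesis.

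SAP 7.1 then gives one concrete precision figure. "A minimum-clinical meaningful cure rate is considered as equal to 70" per cent. For 50 evaluable children in the planned 40/60 severity mix, the SAP claims that "the corresponding 95% CI lower bound of an observed cure rate of 70% would be above ~58" per cent, with a rider that this depends on how far the strata differ. The table above that sentence is headed as the overall cure rate with its 95% CI for N=50. Its cell for 80% cure in light and 55% in moderate/heavy infection reads 70% (58%, 82%).

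The analysis is specified in SAP 16.1.1: "The proportion of responders in each cohort will be determined based on a binomial distribution", and "Exact 95% CIs will be calculated based on the Clopper-Pearson method". SAP 11 adds that where intervals are calculated "these will be two-sided with a confidence probability of 95" per cent. Protocol 8.5 and 8.5.2 name the same Clopper-Pearson method. No stratified interval for the overall cure rate is planned in either document.

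**The concern.** A Clopper-Pearson interval depends only on the number cured and the number analysed. It cannot depend on the difference between strata, so the rider in SAP 7.1 already suggests that the 58% comes from some other calculation. The table points the same way. Two cells share an overall rate of 71% but carry different intervals: (60%, 82%) for 85%/50% and (58%, 82%) for 75%/65%. The planned method would give one interval for both.

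Since nothing is tested, the per-arm estimate and its interval are the main reported inference, and 70% is the trial's own minimum meaningful rate. An arm landing on that threshold will be reported with a lower limit near 55%, and a reader comparing the report with the SAP will find that the promised precision was not met.

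**Working it through.** **Inputs.** N = 50 evaluable, split 20 moderate/heavy and 30 light (40%/60%, SAP 7.1). Observed rate 70%, so x = 35. Two-sided 95% (SAP 11). Clopper-Pearson on the pooled cohort count (SAP 16.1.1; Protocol 8.5, 8.5.2). 60 randomised per arm (SAP 7.1).

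**Step 1: reproduce the plan's figure.** Take the true rates as 55% and 80%, and let X = Bin(20, 0.55) + Bin(30, 0.80). The 2.5% and 97.5% quantiles of X/50 are 58% and 82%, exactly the SAP cell. Applied to the whole table, this matches all 16 lower limits and 14 of 16 upper limits. The two exceptions (75% light with 60% or 65% moderate/heavy) give 82% and 84% against the stated 80% and 82%, a difference of one child. Every limit in the table is a multiple of 1/50, as quantiles of a count out of 50 must be. The table therefore shows where the observed rate may fall for an assumed truth. It is not a set of confidence intervals around an observed rate.

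**Step 2: compute the planned interval.**

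- Lower = Beta quantile(0.025; x, n − x + 1) = Beta quantile(0.025; 35, 16) = 0.554
- Upper = Beta quantile(0.975; x + 1, n − x) = Beta quantile(0.975; 36, 15) = 0.821

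The distance from 70% down to the lower limit is 70 − 55.4 = 14.6 points, against the implied 70 − 58 = 12. The shortfall is 58 − 55.4 = 2.6 points. The upper limit hardly moves (82.1% against 82%).

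**Step 3: could another method rescue 58%?** Lower limits at 35/50, two-sided 95%:

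| Method | Lower limit |
|---|---|
| Clopper-Pearson (planned) | 55.4% |
| Wilson | 56.2% |
| Jeffreys | 56.4% |
| Wald, unstratified | 57.3% |
| Wald, stratified, 80%/55% | 57.8% |

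The stratified figure is 0.70 − 1.96 × √(0.16 × 0.55 × 0.45/20 + 0.36 × 0.80 × 0.20/30) = 0.70 − 1.96 × √0.0039 = 0.578. A stratified Wald limit passes 58% only when the strata differ more widely, for example 83% against 50% (58.1%).

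**Step 4: what would the planned interval need?**

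| Cured/analysed | Observed | Clopper-Pearson lower |
|---|---|---|
| 35/50 | 70% | 55.4% |
| 36/50 | 72% | 57.5% |
| 37/50 | 74% | 59.7% |
| 42/60 | 70% | 56.8% |
| 49/70 | 70% | 57.9% |
| 56/80 | 70% | 58.7% |

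At N = 50 the lower limit first exceeds 58% at an observed 74%. At an observed 70% it takes more than 70 children.

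**Step 5: the rest of the table.** In all 16 cells the stated lower limit is above the Clopper-Pearson limit at the same overall rate, by 0.8 to 3.6 points. For example, 62% is stated as 48–74% against 47–75%, and 74% as 62–86% against 60–85%. At 71% the planned method gives about 56–83% (interpolated, since 71% of 50 is not a whole number).

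**Step 6: the other table.** The probabilities of observing at least 70% all reproduce within 2 points, for example 84.7% against the stated 85% for 85%/60%. That table is sound.

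**The case against.** The strongest reply is that little rests on the 58%. The sentence and its table appear only in SAP 7.1; Protocol 8.1 has neither. Both documents also justify N = 50 by a probability of around 85% of observing at least 70% when the true rate is 75%, and that calculation is correct. The efficacy criterion for dose selection is the observed cure rate, not a confidence limit. No threshold of 58% is used anywhere, and the intervals eventually reported will be valid Clopper-Pearson intervals. The SAP introduces the table as projections under assumed true rates and hedges the bound with an approximation sign and the rider about strata. By the planned Part 1 dates, enrolment would already have finished (December 2017) before this SAP version (31 January 2018), so no arm could be resized.

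All of this limits the consequence and should be accepted. In particular, 58% is not the sole support for the sample size, and the 60-child calculation is a best case, since the mITT set excludes children who need malaria treatment. None of it makes the sentence correct. It describes the confidence limit of an observed rate, which is a different quantity from the one tabulated, and the rider cannot apply to an interval that ignores the strata.

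**Conclusion.** The concern holds. With 50 evaluable children and 35 cured, the planned two-sided 95% Clopper-Pearson interval is 55.4% to 82.1%, so the stated lower bound is about 2.6 points too high. It is not reached with all 60 randomised children either (56.8%). The cause is most likely a mislabelled table: sampling quantiles under assumed true stratum rates were headed as confidence intervals and then read as the interval around an observed 70%. This attribution is inferred from the close match, because the SAP does not describe how the table was made. The 55.4% rests only on N = 50, a 70% observed rate and the method both documents name. The error is in the statement of precision. It does not show that the arms are too small, and it leaves dose selection and the probability table untouched.

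**What to change.** In SAP 7.1, restate the lower bound at an observed 70% with N = 50 as about 55% (exact method) and delete the rider about strata. Then either replace the intervals in the projection table with Clopper-Pearson limits at each overall rate, or keep the numbers and retitle them as the range expected to contain 95% of observed rates under the assumed true stratum rates. The table of probabilities of observing at least 70% can stay as it is.

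If the team wants an interval that uses the stratification, a severity-stratified one with 60/40 weights could be added to SAP 16.1.1 as a supplementary result. This is optional, and in the 80%/55% scenario its lower limit, at about 57.8%, would still fall just short of 58%.

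The cost is one recomputed figure and a revised table or table title. The stated precision becomes slightly less favourable; the sample size, conduct and planned primary analysis do not change.

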## 7.2 Randomisation

Part 1: Treatment allocation will be random and balanced at a ratio of 1:1:1:1:1:1. Randomisation will be stratified by the infection severity (40% moderate/heavy and 60% light infections). After 20 subjects/arm are randomized, the SMC will decide on the inclusion of the 7th arm.

Randomisation will continue for arms C1-C6 at a ratio of 1:1:1:1:1:1 until 40 subjects/arm are randomized.

If the C7 arm is included, randomisation will continue with an allocation ratio of 1:1:1:1:1:1:3 until a total of 60 subjects/arm are randomized in the 7 arms. If C7 arm is not included, the allocation ratio will remain the same (1:1:1:1:1) until a total of 60 subjects/arm are randomized in the 6 arms, as shown below.

Randomisation lists indicating a randomisation number and which treatment is to be given, will be produced prior to the start of the trial by the statistician at the **PPD**...Based on the randomisation lists sequentially numbered sealed envelopes which contain a randomisation number and the treatment allocation will be prepared. The sealed randomisation envelopes will look identical and will be kept in a locked cupboard to which only the study

Part 2: There is no randomisation in this part.

pharmacist will have access.

## 8 Overview of Planned Analyses

The analyses will take part in a staggered manner for the distinct parts of the study, each part being self-contained. Separate appendices of the SAP will cover interim analyses for periodic safety review by the SMC. An overview of the planned analyses is provided below, in the order in which the analyses would be performed.

